2 Baseline bone marrow aspirate and biopsy should be performed within 12 weeks of enrollment. Post therapy marrow will be performed only to confirm complete response, or as clinically indicated. Bone Marrow Studies include aspirate and unilateral biopsy with immunohistochemistry, as well as flow cytometry of the aspirate at baseline and after 2 cycles (baseline and post-cycle 2 cycle marrow aspirates are required for correlative analysis for WM patients).

3 Pregnancy test in women of childbearing potential.

4 CT imaging should be performed within 8 weeks of enrollment. CT neck should also be performed, if cervical adenopathy is present on physical exam. CT scans are repeated at interim analysis or during study protocol treatment for patients with nodal/extramedullary disease at baseline. CT scan should be performed in subjects with nodal/extramedullary disease post-therapy to assess response.

5 For WM patients only, post-cycle 2 bone marrow and flow cytometry studies are required for correlative studies but will not be used for response assessment, which relies on SPEP (for WM) and CT imaging (for MZL). Post-cycle 2 studies may be performed any time after C2D15 dose of CFZ, up until Cycle 3 Day 1.

6 For subjects receiving rituximab with WM, weekly quantitative IgM level (+/- 3 days) is to be measured. Further studies (serum viscosity, CBC, chemistries; additional clinical evaluations) may be performed if hyper-viscosity is suspected. Plasmapheresis may be performed as clinically indicated.

7 Post therapy studies should be done 3 - 5 weeks post cycle 6 or after the patient's last cycle, whichever comes first.

8 Follow-up should be done as per the clinical standard of care. A typical schedule includes every 3 months (total follow-up time from start of drug is 1 year). CT imaging as a standard of care surveillance measure should be performed no more frequently than every 6 months, unless a shorter interval is clinically indicated.

9 Hepatitis B core Ab, Hepatitis B surface Ag; further testing as clinically indicated including HBV DNA

10. Measurement of cardiac ejection fraction within 12 weeks of enrollment, by MUGA, echo, or other invasive/noninvasive testing, is allowed.

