13.0 CORRELATIVE STUDIES

13.1 Assessment of CD19 and CD20 expression changes following CFZ therapy (all patients):

Bortezomib modulates CD20 expression, and affects CDC, in a time- and concentration-dependent manner.^{25, 26} Increased CD20 expression is observed in bortezomib-resistant

cells, which in turn display increased sensitivity to rituximab-mediated complement-dependent cytotoxicity. Furthermore, rituximab resistance appears to depend partly on CD20 down-expression.²⁷⁻³⁰

Therefore, we hypothesize that 1) rituximab-resistant patients will have lower CD20 expression at baseline, and 2) that CFZ may increase CD20 expression after 2 cycles. We will explore, albeit with small sample size of WM patients, whether response to subsequent rituximab in initial CFZ nonresponders is associated with CD20 expression. We postulate that overall, it may be possible to increase CD20 expression to prime tumor cells for optimal rituximab effect, with implications for sequencing these therapies.

Methods: Peripheral blood samples from each patient before therapy and again after 2 cycles of CFZ (see Study Calendar, Section 10.0), will be submitted to UW for quantitative evaluation of CD19 and CD20 surface expression (measuring mean fluorescence intensity).

- 13.2 Correlating Marrow Response Using Flow Cytometry with Paraprotein Response (WM patients only): Response assessment in WM undergoes continual evolution, but still relies on magnitude of the IgM paraprotein reduction. However, discordant responses are commonly observed between paraprotein levels, node size, and marrow involvement and appear to vary based on therapy given. IgM levels have been reported to decrease rapidly with proteasome inhibitors, transiently flare following rituximab, and lag behind marrow responses after fludarabine; best paraprotein response may be delayed, occurring months following therapy.^{22, 31, 32} Flow cytometry is particularly suited for quantifying the lymphoid cells in the marrow of WM patients.^{33, 34} The degree of B cell lymphoid involvement at end of treatment is prognostic—WM patients with less than 5% clonal B cells as in marrow samples by flow cytometry have superior outcomes.³⁵

Methods: Marrow samples from WM patients will be evaluated before treatment, after cycle 2, and at the end of study for patients with CR for flow cytometric evaluation of both lymphoid and plasma cell components, and reported descriptively alongside paraprotein responses.

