20.2 Response Assessment for WM ³⁶

Complete response (CR)

- Absence of serum monoclonal IgM protein by immunofixation
- Normal serum IgM level
- Complete resolution of extramedullary disease, i.e., lymphadenopathy and splenomegaly if present at baseline
- Morphologically normal bone marrow aspirate and trephine biopsy

Very good partial response (VGPR)

- Monoclonal IgM protein is detectable
- $\geq 90\%$ reduction in serum IgM level from baseline*
- Complete resolution of extramedullary disease, i.e., lymphadenopathy/splenomegaly if present at baseline
- No new signs or symptoms of active disease

Partial response (PR)

- Monoclonal IgM protein is detectable
- $\geq 50\%$ but $<90\%$ reduction in serum IgM level from baseline*
- Reduction in extramedullary disease, i.e., lymphadenopathy/splenomegaly if present at baseline
- No new signs or symptoms of active disease

Minor response (MR)

- Monoclonal IgM protein is detectable
- $\geq 25\%$ but $<50\%$ reduction in serum IgM level from baseline*
- No new signs or symptoms of active disease

Stable disease(SD)

- Monoclonal IgM protein is detectable
- $<25\%$ reduction and $<25\%$ increase in serum IgM level from baseline*
- No progression in extramedullary disease, i.e., lymphadenopathy/splenomegaly
- No new signs or symptoms of active disease

Progressive disease (PD)

- $\geq 25\%$ increase in serum IgM level* from lowest nadir (requires confirmation) **and/or**
- progression in clinical features attributable the disease

*This study will employ M protein measurement by densitometry (SPEP) for primary measurement of response.

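### At end of study only, Section 13.2 limits marrow flow to WM patients in CR, so M-protein-negative patients with a morphologically abnormal confirmatory marrow drop out of that descriptive set

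*Combined protocol and SAP*

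**What the plan says.** Section 13.2 gives its reason for the comparison: "discordant responses are commonly observed between paraprotein levels, node size, and marrow involvement and appear to vary based on therapy given". It also singles out the later time point: "The degree of B cell lymphoid involvement at end of treatment is prognostic". The sampling rule is "Marrow samples from WM patients will be evaluated before treatment, after cycle 2, and at the end of study for patients with CR", and results are to be described next to the paraprotein responses, with no test or agreement measure.

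Appendix 20.2 lists four conditions for CR in WM. Two matter here: "Absence of serum monoclonal IgM protein by immunofixation" and "Morphologically normal bone marrow aspirate and trephine biopsy". The other two are a normal serum IgM and resolution of extramedullary disease.

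Footnote 2 to the Section 10.0 calendar is slightly wider than 13.2 on when a late marrow is taken: "Post therapy marrow will be performed only to confirm complete response, or as clinically indicated". On the assay it is narrower, naming "flow cytometry of the aspirate at baseline and after 2 cycles" and no later flow. Footnotes 2 and 5 require the baseline and post-cycle-2 marrows for all WM patients, whatever their response.

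**The concern.** The section wants to see how marrow and paraprotein differ. At its last time point, the rule for entering the set is built partly from those same two measurements. CR cannot be declared until the confirmatory marrow has been read, and an abnormal reading removes the patient from the category that 13.2 evaluates. The patient who leaves is an informative one: paraprotein gone, disease still visible in the marrow. Section 13.2 itself notes that IgM can fall quickly with proteasome inhibitors, so this kind of discordance is plausible with carfilzomib.

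The time point has some value of its own. Rituximab starts in cycle 3 (Section 7.2), so the post-cycle-2 marrow describes two cycles of carfilzomib alone. Only the late sample can describe the full six cycles or the combination. What is at stake is how completely that one descriptive table shows residual marrow disease.

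**Working it through.** The plan gives no figure for this comparison (no sample size, CR rate or error rate), so the check sets the passages side by side.

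**Step 1. Who can enter the end-of-study set.** Cross M-protein status with marrow morphology, then apply the CR definition (20.2), the 13.2 rule and footnote 2.

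| M-protein (immunofixation) | Marrow morphology | Can be CR? | In 13.2 end-of-study set? | Marrow taken under footnote 2? |
|---|---|---|---|---|
| Present | Abnormal | No | No | Only for clinical reasons |
| Present | Normal | No | No | Only for clinical reasons |
| Absent | Abnormal | No | No | Yes, if drawn to check for CR |
| Absent | Normal | Yes, if IgM is normal and extramedullary disease has resolved | Yes | Yes, to check for CR |

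Only the last row enters. Paraprotein is therefore constant in the set, and no relation between it and any marrow measure can be seen there.

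**Step 2. The third row.** This patient's sample exists, but the patient is not in CR. Nor do the response categories below CR fit, since each lists "Monoclonal IgM protein is detectable". Whatever label is given, it is not CR, and the literal wording of 13.2 leaves the sample out because of the marrow result.

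**Step 3. What can still vary.** Section 13.2 measures flow, while CR uses morphology. Residual clonal cells by flow can therefore be present or absent within the last row.

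**Step 4. Direction of the distortion.** Take M-protein-negative patients who meet the other CR criteria and have a confirmatory marrow. Let *a* have abnormal and *b* normal morphology, with flow-positive proportions *p_a* and *p_b*.

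- Proportion visible under 13.2: *p_b*
- Proportion in all such patients: (*a·p_a* + *b·p_b*) / (*a* + *b*)
- Difference, all minus visible: [*a* / (*a* + *b*)] × (*p_a* − *p_b*)

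The difference is zero if no confirmatory marrow is abnormal (*a* = 0). It is positive if morphologically abnormal marrows are flow-positive more often than normal ones. That is an assumption, but a natural one. If every abnormal marrow is flow-positive (*p_a* = 1), the difference is [*a* / (*a* + *b*)] × (1 − *p_b*). The documents give neither *a* nor *b*, so no number follows.

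**Step 5. What is untouched.** The baseline and post-cycle-2 marrows are required in all WM patients, with SPEP scheduled in the same window, so discordance in either direction can be described there. Section 7.2.1 and footnote 5 keep the post-cycle-2 marrow out of response assessment. The primary endpoint and the two-stage design in 12.2 do not depend on the 13.2 set.

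**The case against.** The strongest reply is that the main comparison is already unselected, because all WM patients contribute at baseline and after cycle 2. This stands, and it confines the point to one of three time points.

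A second reply is that 13.2 is about flow, while CR is about morphology. Flow-positive marrow in an immunofixation-negative patient is itself discordance, and 13.2 would record it. This also stands. A reader might infer from the table above that discordance at end of study must be 0% whatever the truth. That holds only for morphology against M-protein, an analysis that 13.2 does not plan.

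Third, no agreement rate or association is specified, so a description within CR is legitimate as depth of response. A reader might infer that the plan will report a false concordance between paraprotein and marrow, but the documents announce no such claim. What remains is that a table of this set, shown without its selection rule, would be easy to misread.

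Fourth, the CR wording in 13.2 may be shorthand for suspected CR. Section 13.3 refuses specimens that are frozen or more than 48 hours old, so the aspirate may have to go for flow before CR is settled, and nothing says that a result is then discarded. This is a fair reading, and it makes the exclusion a consequence of the literal text and not a certainty. If it is what was meant, saying so changes only the wording.

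Finally, using the late marrows already taken does not give a discordance rate. Patients with persistent M-protein and a cleared marrow, the IgM-lag pattern that 13.2 mentions, are still seen only if biopsied for clinical reasons. That is correct, and the set must be labelled accordingly.

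**Conclusion.** The point holds for the end-of-study time point, on a literal reading of 13.2. Within that set paraprotein does not vary, and M-protein-negative patients with a morphologically abnormal confirmatory marrow are left out because of the marrow result, even though the sample was taken. Residual disease in M-protein-negative patients is then probably understated. This rests on two assumptions: that at least one confirmatory marrow is abnormal, and that abnormal marrows are flow-positive more often than normal ones. The amount cannot be stated from the documents.

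The documents do not support the wider reading that 13.2 as a whole excludes discordant patients, since the post-cycle-2 comparison includes them. This is a minor improvement to one exploratory, descriptive time point.

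**What to change.** 1. In 13.2, replace the restriction to CR at end of study with wording such as: *at the end of treatment, for every WM patient in whom a marrow is obtained under footnote 2, whatever the result*. This also matches the calendar, which places the late marrow in the end-of-treatment column.
2. Report flow and morphology next to paraprotein status for each such patient, with the reason for the biopsy.
3. State that the marrow-paraprotein correlation rests on the baseline-to-post-cycle-2 pairs. State that the end-of-treatment samples are a selected descriptive set, in which patients with persistent M-protein and a cleared marrow appear only if biopsied for clinical reasons.
4. Reconcile footnote 2 with 13.2 by adding end-of-treatment aspirate flow, which the footnote does not now list.
5. Send the aspirate for flow when it is drawn. Under the specimen limits in 13.3, flow cannot be added later from frozen or old material.

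The cost is a short edit in two places and a few more flow runs on aspirates already taken. No new biopsy is needed.

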14.0 REPORTING REQUIREMENTS FOR ADVERSE EVENTS/ADVERSE REACTIONS

14.1 Adverse Events Definitions

An AE is any untoward medical occurrence in a study subject administered an investigational product and that does not necessarily have a causal relationship with this treatment.

An AE therefore can be any unfavorable and unintended sign (including laboratory finding), symptom or disease temporally associated with participation in an investigational study, whether or not considered drug-related. In addition to new events, any increase in the severity or frequency of a pre-existing condition that occurs after the subject signs a consent form for participation is considered an AE. This includes any side effect, injury, toxicity, or sensitivity reaction.

An unexpected AE is any adverse drug event, the specificity or severity of which is not consistent with the current IB or prescribing information for a marketed compound. Also, reports which add significant information on specificity or severity of a known, already documented AE constitute unexpected AEs. For example, an event more specific or more severe than described in the IB would be considered "unexpected".

Whenever possible, the most current version of the Common Terminology Criteria for Adverse Events (CTCAE) should be used to describe the event and for assessing the severity of AEs (see Appendix D). Any events representing a change in the CTCAE Grade need to be reported on the AE case report form.

For AEs not adequately addressed in the CTCAE, the severity table below may be used:

| Severity | Description |
|----------------------------|---|
| GRADE 1 – Mild | Asymptomatic or mild symptoms; clinical or diagnostic observations only; intervention not indicated. |
| GRADE 2 – Moderate | Minimal, local or noninvasive intervention indicated; limiting age-appropriate instrumental activities of daily living (preparing meals, shopping, using the phone, managing money, etc.). |
| GRADE 3 – Severe | Medically significant but not immediately life-threatening; hospitalization or prolongation of hospitalization indicated; disabling; limiting self-care activities of daily living (bathing, dressing, feeding self, toileting, taking medications, not bedridden). |
| GRADE 4 – Life-threatening | Life –threatening consequences; urgent intervention indicated. |
| GRADE 5 – Fatal | Death |

Any condition, laboratory abnormality, or physical finding with an onset date prior to the subject signing consent for study participation is considered to be pre-existing in nature and part of the subject's medical history.

Causality

Using the following criteria, the relationship of the AE to the study drug should be assessed as follows:

Yes, the event is suspected to be related if:

- there is a clinically plausible time sequence between onset of the AE and administration of study treatment; and/or
- there is a biologically plausible mechanism for the study treatment to cause or contribute to the AE; and/or
- the event responds to withdrawal of the study medication (de-challenge) and/or recurs with re-challenge (when clinically feasible); and/or

- the AE cannot be reasonably attributed to concurrent/underlying illness, other drugs, or procedures

No, the event is NOT suspected to be related if

- the AE is more likely to be explained by the subject's clinical state, underlying disease, concomitant medication, study or non-study procedure; and/or
- the time of occurrence of the AE is not reasonably related to administration of study treatment; and/or
- the event is unlikely to be related to the investigational product(s)

14.2 Adverse Events Reporting Procedures

All AEs (e.g., any new event or worsening in severity or frequency of a pre-existing condition or laboratory finding) with an onset date after the first dose of study drug must be promptly documented on the appropriate summary. Details of the event must include severity, relationship to study drug, duration, action taken, and outcome. Serious adverse events (SAEs) will be recorded on the appropriate form.

All AEs that are considered related to study drug must be followed to resolution or stabilization if improvement is not expected.

AEs should be reported from the time the subject receives their first dose of study drug, through 30 days post-last dose of study drug or initiation of a new anti-cancer therapy, whichever occurs first. In addition, the Investigator should report any AE that may occur after this time period that is believed to have a reasonable possibility of being associated with study drug. If a subject discontinues study prior to receiving any study drug, AEs must be reported through the end-of-study visit. AEs which completely resolve and then recur should be recorded as a new AE. For subjects who complete the end of study visit less than 30 days following their last dose of study drug, a follow up of ongoing AEs should be attempted by telephone, and documented in the subject's source. AEs continuing at 30 days post-last dose should have a comment in the source by the Investigator that the event has stabilized or is not expected to improve.

The Principal Investigator is responsible for evaluating all AEs, obtaining supporting documents, and determining that documentation of the event is adequate. Adverse events will be assigned a severity grade using the most current version of the NCI-CTCAE.

Grade 3 or higher AE's will be recorded, including laboratory abnormalities. Grade 1 and 2 abnormalities should only be recorded if they require treatment or are otherwise considered clinically significant by the Investigator.

The Principal Investigator may delegate reporting and AE assessment duties to Sub-investigators and must ensure that these Sub-investigators are qualified to perform these duties under the supervision of the Principal Investigator.

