The approved dose of CFZ for relapsed/refractory multiple myeloma is as follows, and employs a priming dose and if tolerated, then escalating to 27 mg/m² (over 10 minutes) when given in combination with lenalidomide and dexamethasone, or escalating CFZ to 56 mg/m² (given over 30 minutes) when given in combination with dexamethasone:

- o CFZ in combination with lenalidomide and dexamethasone
 - o cycle 1: 20 mg/m² over 10 minutes on days 1 and 2; if tolerated, increase dose to 27 mg/m² over 10 minutes on days 8, 9, 15, and 16 of a 28-day treatment cycle
 - o cycles 2-12: 27 mg/m² over 10 minutes on days 1, 2, 8, 9, 15, and 16 of a 28-day treatment cycle

- o cycles 13-18: 27 mg/m² over 10 minutes on days 1, 2, 15, and 16 of a 28-day treatment cycle
 - CFZ in combination with dexamethasone
- o cycle 1: 20 mg/m² over 30 minutes on days 1 and 2; if tolerated, increase dose to 56 mg/m² over 30 minutes on days 8, 9, 15, and 16 of a 28-day treatment cycle
- o cycle 2 and onwards: 56 mg/m² over 30 minutes on days 1, 2, 8, 9, 15, and 16 of a 28-day treatment cycle

Results of CFZ for first-line treatment of WM in combination with rituximab and dexamethasone have recently been published in abstract form. The combination produced a response in 81% of patients, and 22/31 remain on study at 8 cycles of therapy; no neuropathy of grade 2 or higher was seen.¹² However, the single-agent efficacy of CFZ in WM or other NHL is undefined, nor have response-adapted studies--reserving combination therapy with rituximab for non-responders-- been reported.

The dosing of carfilzomib has recently undergone evolution, with implications for patient convenience and the practical administration of therapy. CFZ was historically administered twice weekly, but recent data from multiple myeloma (MM) identified acceptable safety and promising efficacy once weekly administration at the so-called 20/70 dose (CFZ 20 mg/m² over 30 minutes on Cycle 1 Day 1, then 70 mg/m² on D8 and D15 of cycle 1 and all days of future cycles; cycles are repeated every 28 days).¹⁵ In that study, only 12% of patient discontinued therapy due to adverse events. Despite limitations of cross-trial comparisons, adverse event rates were similar or lower than prior twice-weekly studies. This data, in addition to providing the basis for a large upcoming study using weekly carfilzomib in myeloma (NCT#02412878), support the proposed weekly dosing in this trial.

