12.3 Stopping Rule, and Rules for Suspending Accrual

12.3.1 Futility: The study will be stopped if two or fewer of the first 9 patients respond after cycle two, as in section 12.2 above.

12.3.2 Cardiac Toxicity: A composite endpoint of cardiotoxicity will lead to suspension of accrual, at the thresholds noted below: myocardial infarction, new onset atrial fibrillation, cerebrovascular accident, grade 4 hypertension, grade 3 left ventricular dysfunction, or grade 2 or higher heart failure. Events are counted per patient (i.e. a patient with more than one cardiac event counts only once toward this limit.)

If there is sufficient evidence to suggest that the occurrence of any of the components of this composite "toxicity" (occurrence of at least one will constitute a "toxicity") exceeds a frequency of 10% of accrued patients, study accrual will be suspended pending review by the institutional data safety monitoring committee. Further accrual may be undertaken only with approval of that committee. Sufficient evidence will be taken to be any observed ratio associated with a lower 80% one-sided confidence limit that exceeds 0.10.

Operationally, any of the following proportions of accrued patients experiencing cardiac toxicity (as defined above) would yield such a ratio: 2 of the first 8 or fewer patients, 3 of the first 15 or fewer patients, 4 of the first 23 or fewer patients.

If the true probability of toxicity is .05, the probability of stopping after 15 or 23 patients is approximately .08 and .08, respectively. If the true probability of toxicity is .25, the probability of stopping after 15 or 23 patients is approximately .81 and .90, respectively (probabilities of stopping estimated from 5,000 simulations).

12.3.3 Inability to deliver rituximab therapy as per protocol:

If per-protocol rituximab (as per protocol section 7.2) cannot be administered to at least 6 of the first eligible 12 patients for any reason, accrual will be suspended for review by the institutional data safety monitoring committee, before further accrual may proceed.

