15.0 DATA AND SAFETY MONITORING PLAN

Ongoing trial oversight is carried out by the Principal Investigator. The Principal Investigator will review acquired data and adverse events on a regular basis. The data recorded within the research charts and protocol database is compared with the actual data that is available from the medical record and/or clinical histories. Data detailed in the research case report forms includes the nature and severity of all toxicities, which are also reported as described above.

Institutional support of trial monitoring will be in accordance with the FHCRC/University of Washington Cancer Consortium Institutional Data and Safety Monitoring Plan. Under the provisions of this plan, Fred Hutchinson Cancer Research Center (FHCRC) Clinical Research Support coordinates data and compliance monitoring conducted by consultants, contract research organizations, or FHCRC employees unaffiliated with the conduct of the study. Independent monitoring visits occur at specified intervals determined by the assessed risk level of the study and the findings of previous visits per the institutional DSMP.

In addition, protocols are reviewed at least annually and as needed by the Consortium Data and Safety Monitoring Committee (DSMC), FHCRC Scientific Review Committee (SRC) and the FHCRC/University of Washington Cancer Consortium Institutional Review Board (IRB). The review committees evaluate accrual, adverse events, stopping rules, and adherence to the applicable data and safety monitoring plan for studies actively enrolling or treating patients. The IRB reviews the study progress and safety information to assess continued acceptability of the risk-benefit ratio for human subjects. Approval of committees as applicable is necessary to continue the study.

The trial will comply with the standard guidelines set forth by these regulatory committees and other institutional, state and federal guidelines.

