18.0 TERMINATION OF THE STUDY

Patients may be removed from this study at any time per their discretion. Individual patients may be removed from this protocol if they develop any untoward side effects from the study treatment or for other reasons as described under section 7.7.

The study will be closed to accrual upon treatment of the total planned number of study subjects. The study will be completed following treatment of all study subjects and completion of follow-up and data analysis as described in the protocol. If the study drug becomes unavailable for any reason, the study will be suspended until drug availability resumes or terminated as appropriate. In addition, there are stopping rules in place for lack of efficacy as detailed in the statistical section. The Principal Investigator may terminate the study at any time. The IRB and FDA also have the authority to suspend or terminate the study should it be deemed necessary.

The Principal Investigator shall provide Amgen with a final study report no later than **one (1) calendar year** after study completion. The report shall include all AEs generated by the Study, irrespective of whether the AEs are serious or non-serious, and a causality assessment for each AE, regardless of whether the AE is related to the investigational drug.

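### Section 14.2 asks for all adverse events and then filters out some grade 1-2 events, in conflict with 14.1, 15.0 and 18.0, so low-grade neuropathy may be recorded selectively

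*Combined protocol and SAP*

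**What the plan says.** Two recording rules stand in section 14.2. Its first paragraph covers all adverse events "with an onset date after the first dose of study drug must be promptly documented on the appropriate summary", with no grade limit. Further down, the same section states "Grade 3 or higher AE's will be recorded, including laboratory abnormalities", followed directly by "Grade 1 and 2 abnormalities should only be recorded if they require treatment or are otherwise considered clinically significant by the Investigator".

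Three other sections bear on the same data:

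- Section 14.1: "Any events representing a change in the CTCAE Grade need to be reported on the AE case report form".
- Section 15.0: "Data detailed in the research case report forms includes the nature and severity of all toxicities".
- Section 18.0, on the final study report: "The report shall include all AEs generated by the Study, irrespective of whether the AEs are serious or non-serious". It also asks for a causality assessment of each event.

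Two parts of the plan use low-grade events. Objective 1.2.1 is the safety and tolerability of weekly carfilzomib, alone and with rituximab. Section 12.3.2 suspends accrual on a composite of "myocardial infarction, new onset atrial fibrillation, cerebrovascular accident, grade 4 hypertension, grade 3 left ventricular dysfunction, or grade 2 or higher heart failure", counted once per patient.

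**The concern.** A site cannot both document every adverse event and leave out the grade 1-2 events that nobody treats. Which rule it follows decides what the safety tables contain.

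Neuropathy is where this matters most. Section 2.1 gives a lower risk of neuropathy than with bortezomib as part of the case for carfilzomib. Patients may enter with painless grade 2 neuropathy, since 5.2 excludes only grades 3-4 or grade 2 with pain, and 5.3.1 lists neuropathy due to Waldenström's among the indications for treatment. The dosing table in 8.2.4 refers to treatment-emergent neuropathy and to return to baseline. Separating new from pre-existing neuropathy needs the low grades on record. If they are kept at the investigator's discretion in an open-label, single-arm trial, the low-grade counts reflect reporting habits as well as toxicity.

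**Working it through.** The plan gives no figure for this point, so the check is mainly of text.

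**1. The recording rules side by side**

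| Place | What must be captured | Met if the grade 1-2 filter is applied to clinical events? |
|---|---|---|
| 14.2, first paragraph | All adverse events after first dose | No |
| 14.1 | Every change of CTCAE grade | No: an untreated move from grade 1 to grade 2 could be omitted |
| 15.0 | All toxicities, with severity | No |
| 18.0 | All adverse events, serious or not | No |
| 14.2, later sentences | Grade 3 or higher; grade 1-2 if treated or judged significant | Yes (this is the filter) |

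**2. Two readings of the grade 1-2 sentence.** It speaks of abnormalities, and the sentence before it ends on laboratory abnormalities, so a laboratory-only meaning is possible. But that preceding sentence sets grade 3 as the threshold for adverse events generally and names laboratory findings as a subset. If clinical events of every grade were to be recorded anyway, that threshold would do no work for them. The text does not settle the matter.

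**3. Neuropathy by grade, if the filter covers clinical events**

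- Grade 3 or 4: recorded.
- Grade 2 with pain: has its own row in the 8.2.4 dosing table, so it must be followed and is hard to call insignificant.
- Grade 2 without pain, untreated: recorded only if judged significant.
- Grade 1, untreated: recorded only if judged significant.

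**4. The 12.3.2 composite, component by component**

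| Component | Route to capture despite the filter |
|---|---|
| Grade 4 hypertension | Passes the grade 3 threshold |
| Grade 3 left ventricular dysfunction | Passes the grade 3 threshold |
| Myocardial infarction, cerebrovascular accident | Would ordinarily meet a serious-event criterion in 14.3 and be reported under 14.4 |
| Heart failure from grade 2 | Symptoms compel a dose hold under 8.2.4, so omission is unlikely |
| New atrial fibrillation, no grade floor | If low-grade, untreated and not serious: investigator judgment only |

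**5. The cardiac rule's own figures.** These are not disputed. The exact one-sided 80% lower limit is the 20th percentile of Beta(x, n − x + 1). It gives 0.1044 for 2/8, 0.1041 for 3/15 and 0.1015 for 4/23, all above 0.10. One patient later (2/9, 3/16, 4/24) it gives 0.0926, 0.0975 and 0.0972, all below. An exact binomial recursion with these limits gives these probabilities of stopping by 15 and 23 patients:

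| True rate | Recomputed | Stated in 12.3.2 |
|---|---|---|
| .05 | 0.072 and 0.080 | .08 and .08 |
| .25 | 0.805 and 0.901 | .81 and .90 |

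The agreement is close. Both sets of figures take every qualifying patient as counted. With limits of 2, 3 and 4 patients, one uncounted patient could decide a suspension, but the documents give nothing from which to estimate how often that would happen.

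**The case against.** The best defence is that the filter was meant for laboratory values. Clinical events of every grade would then fall under the first paragraph of 14.2, in agreement with 14.1, 15.0 and 18.0, and only the wording would need tidying. This is a fair reading and may well be the intended one. It does not explain the grade 3 threshold set for adverse events in the sentence before, and staff could reasonably work to either rule.

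Three stronger conclusions might be inferred, and the documents do not support them:

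- **That the cardiac rule will undercount materially.** Most components reach the record by another route. Section 12.3.2 does not say that its count is drawn from the 14.2 record. New atrial fibrillation is also a named trigger, which an investigator applying this protocol would find hard to dismiss. A narrow gap is all that remains.
- **That neuropathy results will be biased against a benchmark.** Section 2.1 does report of an earlier combination study that "no neuropathy of grade 2 or higher was seen", but as background. No objective, endpoint or analysis compares this trial with it.
- **That the loss can be quantified.** Any figure would need the share of low-grade events left unrecorded. The documents give none, and a chosen share would be invented.

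**Conclusion.** The contradiction is in the text and should be corrected. If sites apply the filter to clinical events, untreated grade 1 neuropathy and painless, untreated grade 2 neuropathy are recorded at the investigator's discretion. The low-grade safety data for objective 1.2.1 become selective, and the report promised in 18.0 cannot be complete. The exposure of the cardiac rule is small and lies mainly in untreated low-grade new atrial fibrillation. No numerical magnitude is attached.

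The conclusion rests on one assumption: that some staff would read the later sentences of 14.2 as covering clinical events, which the wording permits. The primary endpoint and the sample size are unaffected.

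**What to change.** - State a single recording rule in 14.2 that agrees with 14.1, 15.0 and 18.0.
- Limit the grade 1-2 filter in express words to isolated laboratory abnormalities.
- Require neuropathy of any grade, and every event that meets the 12.3.2 composite definition, to be recorded whether or not it is treated. The adverse event assessments already in the section 10.0 calendar (pre-entry, day 1 of each cycle, end of treatment) are enough.
- Leave the commitment in 18.0 as it stands. Narrowing it to whatever was recorded would fit the report to the filter instead of removing the conflict.

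The cost is a wording change and a few more case report form entries per patient. No visit or test is added, and no dose or clinical rule changes.
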